3. SAMPLE SIZE DETERMINATION

The primary objective of this study is to evaluate the antiviral activity of AT-527 compared with placebo. Approximately 60 patients will be randomized in a 1:1 ratio in Cohort A to receive AT-527 or placebo. Each additional cohort will enroll approximately 40 patients in a 3:1 ratio to receive AT-527 or placebo, respectively.

The sample size is based on the primary endpoint of change from baseline in SARS-CoV-2 virus RNA measured by RT-PCR at a single timepoint. A sample size of

27 patients per treatment group (active or placebo) in the modified intent-to-treat infected (mITTi; defined in [Table 2](#)) population will result in at least 80% power to detect a mean reduction in change from baseline of between 0.7 and 1.1 log₁₀ copies using a two-sample t-test for comparison of means, assuming a standard deviation of between 1.2 and 1.85 (Regeneron 2020) and based on a 1-sided 10% alpha. The sample size has been adjusted to 30 patients per treatment group to account for an estimated 90% SARS-CoV-2 positive rate and is based on a single-cohort comparison of AT-527 versus placebo.

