5.4 SECONDARY ENDPOINTS ANALYSES

All secondary endpoints will be analyzed descriptively and summary statistics will be presented. Descriptive comparisons will be made for each AT-527 group and a pooled placebo group containing patients from all cohorts. For time to event endpoints, a Kaplan-Meier plot and the median time to response will be presented along with the 80% CI. For proportion, frequency and incidence endpoints, the number, proportion and difference in proportions along with 80% CIs will be presented. For area under the curve (AUC) endpoints, summary statistics will be presented.

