5.4.1 Potential Further Statistical Analyses

If required, in addition to the descriptive analyses, formal statistical analysis may also be presented for secondary endpoints.

Time to event secondary virology and efficacy endpoints may be analyzed using the generalized Wilcoxon test or log-rank test (as appropriate), which may be stratified for appropriate covariates. Secondary proportion, frequency and incidence endpoints for virology and efficacy may be analyzed using the Fisher's Exact test. AUC and duration secondary endpoints may be analyzed using the Mann-Whitney U test, where AUC is calculated using the trapezoidal method.

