5.4.2 Secondary Endpoints

5.4.2.1 Secondary Endpoints (Virology)

All secondary virology analyses will be performed on the mITTi population.

All virology analyses will be performed using the nasopharyngeal swab data.

Descriptive analyses of saliva and serum samples will be performed on an exploratory basis for the primary and secondary virology endpoints, as required.

Time to event virology secondary endpoints

For time to event virology secondary endpoints, time will be calculated in hours.

- **Time to cessation of SARS-CoV-2 viral shedding as measured by RT-PCR**
 - Time to cessation of viral shedding by RT-PCR, in hours, is defined as the time between the initiation of any study treatment and first time when a negative or BLQ test result by RT-PCR is obtained. Patients who do not receive a negative or BLQ test result by RT-PCR by the last observation timepoint will be treated as censored at the final timepoint on Day 7.
- **Time to sustained non-detectable SARS-CoV-2 virus RNA**
 - Time to sustained non-detectable SARS-CoV-2 virus RNA, in hours, is defined as the time between the initiation of any study treatment and first time when a negative or BLQ test result by RT-PCR is obtained after which no positive test above or equal to the LOQ was reported. Patients who do not meet this endpoint by the last observation timepoint will be treated as censored at the final timepoint on Day 7.

These time-to-event endpoints will be summarized using descriptive statistics by treatment, as well as Kaplan-Meier plots. The median time to response from the Kaplan-Meier plots will be presented along with the 80% CI. If required, a hazard ratio may be produced adjusting for baseline viral load using a Cox proportional hazards model.

For all cohorts, the virology time-to-event endpoints will be described for the AT-527 group and the pooled placebo group through Day 7 using the mITTi population.

For virology time to event endpoints, deaths will be right censored at Day 7. Consequently, for these endpoints, participants censored on the final day reflect two different states, death or failure to meet the improvement outcome criterion. Therefore, it is important to understand the outcome in the context of the number and timing of deaths by treatment group.

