Intercurrent events are those that occur after treatment initiation and either preclude observation of the variable or affect its interpretation. Intercurrent events and missing data will be accounted for through censoring rules, as described in [Table 7](#) below.

Table 7 Virology Time to Event Censoring

Event	Censor	Date and Time
Death prior to meeting endpoint	Yes	Final timepoint on Day 7
Discontinuation or lost to follow-up up to Day 7 for any reason prior to meeting endpoint	Yes	Last observed virology assessment
Do not meet the endpoint	Yes	Final timepoint on Day 7

Proportion virology secondary endpoint

- **Proportion of patients positive for SARS-CoV-2 virus RNA by RT-PCR at specified timepoints**
 - Proportion of patients positive for SARS-CoV-2 virus RNA by RT-PCR will be presented by treatment at each visit. It is defined as the percentage of patients with a positive virus RNA by RT-PCR test result above or equal to the LOQ.

For virology proportion endpoints in all cohorts, the proportion of patients positive for SARS-CoV-2 virus RNA by RT-PCR will be compared between the AT-527 group and the combined placebo group. For all cohorts, the number, proportion and difference in proportions along with 80% CIs will be presented by treatment group for all timepoints.

Missing data will be treated as missing and will not be included in the analysis. However, if a patient dies, the non-responder rule will apply and the patient will be imputed as positive for all timepoints post-death.

Area under the curve (AUC) virology secondary endpoint

- **Area under the curve in the amount of SARS-CoV-2 virus RNA as measured by RT-PCR**
 - AUC in virus RNA (RT-PCR) will be presented by treatment group and is defined as AUC of the amount of virus RNA (RT-PCR). AUC will be calculated using the trapezoidal method. AUC of change from time 0 (t_0) to time K (t_k) is given by the formula:

$$\sum_{k=1}^K \frac{(y_k + y_{k-1})(t_k - t_{k-1})}{2},$$

where t_k (hours) represents the date of the k^{th} virus RNA (RT-PCR) assessment ($k = 0, \dots, K$) and y_k represents the \log_{10} value of the k^{th} virus RNA (RT-PCR) assessment.

For the virology AUC endpoint, the AUC of the amount of virus RNA (RT-PCR) will be compared between the AT-527 group and a combined placebo group. For all cohorts, summary statistics will be presented to Day 7 using the full combined placebo group.

Missing data will be treated as such and not included in the analysis.

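### The secondary viral-load AUC is built from raw levels and compared without baseline viral load, the covariate that the primary analysis adjusts for

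*SAP*

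**What the plan says.** SAP 5.4.2.1 defines the endpoint: "AUC in virus RNA (RT-PCR) will be presented by treatment group and is defined as AUC of the amount of virus RNA (RT-PCR". The formula that follows is introduced with the words "AUC of change from time 0", but its terms are log10 values of each assessment, not changes, and the sum starts at assessment 0. By SAP Table 4 that is the Day 1 pre-dose swab. The section says the area is to be compared with the combined placebo group.

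The tools for that comparison are limited. SAP 5.4 says: "For area under the curve (AUC) endpoints, summary statistics will be presented". SAP 5.4.1 adds, only if required: "AUC and duration secondary endpoints may be analyzed using the Mann-Whitney U test, where AUC is calculated using the trapezoidal method". Neither section names a covariate for the AUC, and protocol 6.4.2 adds none.

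Elsewhere the plan does use baseline viral load. It is the covariate of the primary ANCOVA (SAP 5.3.2, protocol 6.4.1) and defines a subgroup (SAP 5.3.5). For the virology time-to-event endpoints SAP 5.4.2.1 says: "If required, a hazard ratio may be produced adjusting for baseline viral load using a Cox proportional hazards model".

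**The concern.** Baseline enters this area twice: directly, as the first point of the trapezoid, and indirectly, because patients who start high tend to stay high. An unadjusted comparison therefore mixes any drug effect with the difference in starting viral load between the groups.

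Such differences are plausible. Protocol 4.2.1 describes permuted blocks and names no stratification by viral load. Symptom onset may be up to five days before randomization, and the mITTi population needs a quantifiable swab only at some point in the study. Under the SAP the placebo group is pooled over cohorts enrolled one after another, so a baseline difference may be systematic as well as due to chance.

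At stake is how a listed secondary antiviral endpoint will be read. A gap in mean AUC could be taken as drug effect when part of it is baseline, and a real effect could be hidden by variance that a collected covariate would remove.

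**Working it through.** **The plan's own figure.** The SAP sizes the primary endpoint for "at least 80% power to detect a mean reduction in change from baseline of between 0.7 and 1.1" log10 copies, "assuming a standard deviation of between 1.2 and 1.85", "based on a 1-sided 10% alpha". With n per group = 2(1.2816 + 0.8416)² × (SD/effect)²:
- 0.7 with SD 1.2 gives 26.5, so 27; t-test power at 27 is 80.1%.
- 1.1 with SD 1.85 gives 25.5, so 26; power at 27 is 81.2%.
- 27/0.90 = 30.

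The stated size reproduces. The documents give no power or precision figure for the AUC.

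**Structure of the AUC.** Swabs on Days 1, 3, 5 and 7 are nominally at 0, 48, 96 and 144 h. The trapezoid is

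AUC = 24·y0 + 48·y3 + 48·y5 + 24·y7 = 144·y0 + 48·c3 + 48·c5 + 24·c7,

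where c is change from baseline. This step needs no assumption.

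**Inputs for size.**
- From protocol 6.1 (Cohort E): SD of change 1.25, effect 0.5 log10.
- Assumed: baseline SD 1.5 (range 1.0 to 2.0); correlation of baseline with change −0.3 (range 0 to −0.5); correlation between changes at different visits 0.6; the same 0.5 effect at Days 3, 5 and 7.

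**Base case.**
- Effect on AUC: 0.5 × (48 + 48 + 24) = 60 log10·h.
- Variance from baseline: 144² × 1.5² = 46,656.
- Variance from the changes: 1.25² × (5,184 + 2 × 0.6 × 4,608) = 16,740.
- Covariance term: 2 × 144 × 120 × (−0.3) × 1.5 × 1.25 = −19,440.
- Total 43,956, so the unadjusted SD is 209.7.
- Slope on baseline: 144 + 120 × (−0.3) × 1.25/1.5 = 114. Explained variance: 114² × 1.5² = 29,241, or 67%.
- Residual 14,715, so the adjusted SD is 121.3.

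**Power at 27 per arm, one-sided 10%.** The SEs are 209.7 × √(2/27) = 57.1 and 121.3 × √(2/27) = 33.0. Power is Φ(60/57.1 − 1.2816) = 41% unadjusted and Φ(60/33.0 − 1.2816) = 70% adjusted.

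**Over the assumed ranges, 27 per arm.**

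| Baseline SD, correlation | Variance explained | Unadjusted power | Adjusted power | AUC shift from a one-SE baseline imbalance |
|---|---|---|---|---|
| 1.0, −0.5 | 30% | 68% | 79% | 19 log10·h (31% of effect) |
| 1.5, −0.3 | 67% | 41% | 70% | 47 log10·h (78%) |
| 2.0, 0 | 83% | 28% | 66% | 78 log10·h (131%) |

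**Pooled placebo.** Placebo from Cohorts A–D is 30 + 3 × 10 = 60, or 54 at 90% positive. For 27 against 54, the base-case SEs are 49.4 and 28.6, and power is 47% against 79%. A one-SE baseline imbalance is 1.5 × √(1/27 + 1/54) = 0.35 log10 and shifts the AUC by 114 × 0.35 = 40 log10·h.

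**Other correlation models.** These assume equal SDs at all visits.
- Equal correlation 0.3, 0.5 or 0.7 between levels: baseline explains 35%, 53% or 72% of AUC variance.
- First-order autoregressive, adjacent-visit correlation 0.5 to 0.8: 34% to 67%.
- No correlation between baseline and later levels: 10%, because baseline itself carries 1/6 of the weight.
- Simulation of the Mann-Whitney test at 27 per group: power 65%, 54% and 43% at correlations 0.3, 0.5 and 0.7, for effects where the ANCOVA has about 80%.

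**The case against.** The strongest reply is that nothing inferential hangs on this endpoint. SAP 5.4 makes all secondary endpoints descriptive, tests are run only if required, and no interval is planned for an AUC difference. The power figures thus describe a test that may never be run. That stands, and it limits the point to estimation and interpretation. The means will still be set side by side as evidence of antiviral activity, so a baseline gap still matters.

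Second, the size rests on inputs the documents do not give. That also stands. The base case implies a baseline-to-later correlation of about 0.69, near the top of the 0.3 to 0.7 used in the other models. The power figures use normal theory and ignore the imputed values of 60 and 119 copies/mL. The protocol gives one effect size with no time course.

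Third, baseline-adjusted results already exist, since the primary ANCOVA uses the same swabs. It does so visit by visit, not for the area. The time-weighted average change in SAP 5.3.4 is optional, exploratory and has no covariate. At equal correlation 0.3 it has 1.34 times the variance of the raw area, and at 0.5 it has 0.74 times.

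Two stronger readings are tempting. A reader might infer a fall in power from 94% to 53%, which is the base case at 100 per arm and one-sided 2.5%. That is the protocol's Cohort E. This SAP describes Cohort E as 40 patients at 3:1 with 10% alpha. A reader might also extend the point to the proportion-positive endpoint, which is likewise unadjusted. There adjustment removes only 3% to 31% of the variance (correlation 0.3 to 0.7, positive rate 50% to 90%), so it is at most an optional refinement.

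**Conclusion.** The point holds for the AUC. The plan leaves out of this comparison a covariate that it uses for the primary endpoint and foresees for another secondary one, and it gives no reason. That baseline enters the area follows from the formula alone. The size does not: baseline may explain anywhere from 10% of AUC variance (no correlation with later levels) through 34% to 72% (moderate to strong correlation) to 83% (the top of the assumed ranges). In the base case, power at 27 per arm is 41% against 70%, and over the ranges 28–68% against 66–79%.

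A reader might infer that most of the endpoint's precision is certainly lost, or that a formal antiviral claim is undermined. The documents support neither: they give no baseline SD or correlations, and they attach no decision rule to the AUC. This is a worthwhile and nearly free improvement to a descriptive secondary endpoint.

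**What to change.** In SAP 5.4.1 and 5.4.2.1:
- Report the AUC difference from an ANCOVA with baseline log10 viral load as covariate, as a least squares mean difference with the cohort's confidence level (80% in the SAP; protocol 6.4.1 uses 95% for Cohort E).
- Keep the descriptive summaries, and keep Mann-Whitney as an unadjusted check.
- Reword the sentence that introduces the formula so that it describes an area of levels, as the formula does.

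The cost is a few lines of SAP text and code. Baseline viral load is already collected for the primary analysis.

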5.4.2.2 Secondary Endpoints (Safety)

The safety objective for this study is to evaluate the safety of AT-527 compared with placebo.

The safety population will be used for all safety analyses. Patients will be analyzed according to the treatment they actually received.

Safety analyses will be presented by each AT-527 dose and a combined placebo group containing patients from all cohorts. Safety will be assessed through summaries of exposure to study treatment, AEs, changes in laboratory test results, and changes in vital signs and ECGs. If a low number of events is observed, a listing may be produced in place of a summary table. A listing of pregnancies will also be produced.

Study treatment exposure (such as treatment duration and total dose received) will be summarized with descriptive statistics.

- **Incidence and severity of AEs, with severity determined according to NCI CTCAE v5.0**

All verbatim AE terms will be mapped to Medical Dictionary for Regulatory Activities (MedDRA) thesaurus terms and will be classified by System Organ Class (SOC) and preferred term. AE severity will be graded according to NCI CTCAE v5.0. For AEs of varying severity, the highest grade will be used in the summaries. Deaths and cause of death will be listed.

Only treatment-emergent AEs will be summarized. Treatment-emergent AEs are defined as those AEs with observed or imputed onset date on or after the start date of trial treatment. Only where the most extreme intensity is greater than the initial intensity (or if most extreme intensity is not missing and initial intensity is missing) will events with an onset date prior to the start of study treatment be considered treatment-emergent.

An AE with a completely missing start date will be assumed to be treatment-emergent unless the AE has a complete non-imputed end date that is prior to study Day 1. AEs will be coded and tabulated by SOC and/or Preferred Terms (PTs). In tabulations, PTs

and their associated SOC will be presented in order of descending frequency summed across the treatment groups.

The following will be summarized for each AT-527 group and a pooled placebo group, and listings produced where required:

- AEs
- SAEs
- AEs related to study treatment
- AEs leading to death
- AEs leading to withdrawal of study drug
- AEs leading to withdrawal from study
- AEs occurring in $\geq 5\%$ of patients in at least one treatment group
- AEs occurring in $\geq 10\%$ of patients in at least one treatment group
- AEs of NCI CTCAE Grade 3 or higher
- AEs by most extreme NCI CTCAE grade
- AEs and SAEs by outcome
- AEs and SAEs by time of onset according to the following categories:
 - Week 1 (Days 1-7)
 - Week 2 (Days 8-14)
 - Days ≥ 15

All adverse events of special interest (AESI) will be presented by treatment group. AESI are as follows for this study:

- Cases of potential drug-induced liver injury that include an elevated alanine transaminase (ALT) or aspartate aminotransferase (AST) in combination with either an elevated bilirubin or clinical jaundice, as defined by Hy's Law (as detailed in protocol)
- Suspected transmission of an infectious agent by the study drug, as defined below Any organism, virus, or infectious particle (e.g., prion protein transmitting transmissible spongiform encephalopathy), pathogenic or non-pathogenic, is considered an infectious agent. A transmission of an infectious agent may be suspected from clinical symptoms or laboratory findings that indicate an infection in a patient exposed to a medicinal product. This term applies only when a contamination of the study drug is suspected.

Details of any deaths will be presented in the form of an individual patient listing, as well as in a frequency table by treatment group.

- **Change from baseline in targeted vital signs, including peripheral capillary oxygen saturation (SpO₂)**

For each of the vital signs (pulse rate, respiratory rate, blood pressure, peripheral capillary oxygen saturation [SpO₂], and temperature), summary statistics on absolute value and the change from baseline will be presented over time. For all cohorts, this will be presented by treatment group at all timepoints using a combined placebo group containing patients from all cohorts.

Additionally, for all cohorts, a graphical representation of means over time of temperature (daily to Day 28) will be presented. Summaries of other temperature related secondary efficacy endpoint are described in Section 5.4.2.3.

Baseline is defined as the last assessment prior to treatment.

- **Change from baseline in targeted clinical laboratory test results**

For each of the hematological and biochemical test parameters, summary statistics of observed and change from baseline values at each timepoint will be presented by treatment group for each scheduled timepoint. Baseline is defined as the last assessment prior to treatment.

Additionally, shift tables of selected laboratory tests will be used to summarize the baseline and maximum post-baseline severity grade. NCI CTCAE v5.0 grading will be used with an indication of the direction of the abnormality (High, Low). A summary of the number and percentage of patients with abnormal laboratory outcomes will be produced by treatment group and pooled placebo group for each parameter for each scheduled timepoint.

The number and proportion of patients who meet the pre-specified criteria shown in [Table 8](#) will be presented by treatment group during the study.

Table 8 Pre-specified Treatment-Emergent Abnormal Laboratory Criteria

AST (U/L) or ALT (U/L) and Total bilirubin (mg/dL)
AST (U/L) or ALT (U/L) > 3 × Baseline
AST (U/L) or ALT (U/L) > 5 × Baseline
AST (U/L) or ALT (U/L) > 3 × Baseline and Total bilirubin (mg/dL) > 2 × ULN

ALT= alanine aminotransferase; AST= aspartate aminotransferase; ULN= upper limit of normal.

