4.1.2 Exclusion Criteria

Patients who meet any of the following criteria will be excluded from study entry:

- Clinical signs indicative of COVID-19 illness requiring hospitalization, defined as any of the following: shortness of breath at rest, respiratory rate ≥ 30 , heart rate ≥ 125 , peripheral capillary oxygen saturation (SpO_2) $\leq 93\%$ on room air
- Treatment with a therapeutic agent against SARS-CoV-2 including, but not limited to, other direct-acting antivirals, convalescent plasma, monoclonal antibodies against SARS-CoV-2, or intravenous immunoglobulin within 3 months or less than 5 drug-elimination half-lives (whichever is longer) prior to screening
- Requirement, in the opinion of the investigator, for any of the prohibited medications during the study
- Use of hydroxychloroquine or amiodarone within 3 months of screening
- Pregnant or breastfeeding, or intending to become pregnant during the study or within 30 days after the final dose of study drug. Women of childbearing potential must have a negative pregnancy test result at screening
- Abnormal laboratory test results at screening, defined as meeting any of the following sets of criteria:
 - ALT or AST $> 5 \times$ upper limit of normal (ULN)
 - Total bilirubin $> 1.5 \times$ ULN, unless the patient has known Gilbert disease
 - Creatinine clearance $< 60 \text{ mL/min}$ (*Cockcroft-Gault formula*)
 - Total WBC $< 2,500/\text{mm}^3$ or ANC $< 800/\text{mm}^3$
 - Platelet count $< 80 \times 10^9/\text{L}$
- Clinically significant abnormal ECG, as determined by the Investigator, at screening
- Planned procedure or surgery during the study
- Known allergy or hypersensitivity to study drug or drug product excipients
- Substance abuse, as determined by the investigator, within 12 months prior to screening
- Poor peripheral venous access
- Malabsorption syndrome or other condition that would interfere with enteral absorption
- Any clinically significant history of epistaxis within the last 3 months and/or history of being hospitalized due to epistaxis of any previous occasion
- History of anaphylaxis
- Any uncontrolled serious medical condition or other clinically significant abnormality in laboratory tests that, in the investigator's judgment, precludes the patient's safe participation in and completion of the study

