5.3.5.6 Abnormal Liver Function Tests

The finding of an elevated ALT or AST ($>3 \times$ baseline value) in combination with either an elevated total bilirubin ($>2 \times$ ULN) or clinical jaundice in the absence of cholestasis or other causes of hyperbilirubinemia is considered to be an indicator of severe liver injury (as defined by Hy's Law). Therefore, investigators must report as an adverse event the occurrence of either of the following:

- Treatment-emergent ALT or AST $>3 \times$ baseline value in combination with total bilirubin $>2 \times$ ULN (of which $\geq 35\%$ is direct bilirubin)
- Treatment-emergent ALT or AST $>3 \times$ baseline value in combination with clinical jaundice

The most appropriate diagnosis or (if a diagnosis cannot be established) the abnormal laboratory values should be recorded on the Adverse Event eCRF (see Section 5.3.5.4) and reported to the Sponsor immediately (i.e., no more than 24 hours after learning of the event), either as a serious adverse event or an adverse event of special interest (see Section 5.4.2).

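### SAP Table 8's combined liver row omits the protocol's direct-bilirubin condition, and its transaminase flags are scaled only to baseline

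*SAP*

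**What the plan says.** SAP Section 5.4.2.2, Table 8, lists three treatment-emergent laboratory criteria, to be tabulated as number and proportion of patients by treatment group:

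- Row 1: "AST (U/L) or ALT (U/L) > 3 × Baseline"
- Row 2: "AST (U/L) or ALT (U/L) > 5 × Baseline"
- Row 3 (combined): "AST (U/L) or ALT (U/L) > 3 × Baseline and Total bilirubin (mg/dL) > 2 × ULN"

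Baseline is the last assessment before treatment.

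Protocol 5.3.5.6 has two reporting bullets for liver tests. The laboratory bullet has the same two thresholds as Row 3, with the further condition that at least 35% of the total "is direct bilirubin". The other bullet pairs the same transaminase threshold with clinical jaundice. Both scale ALT and AST to baseline.

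Protocol 4.1.2 excludes ALT or AST above 5 × ULN at screening and sets no lower limit. It excludes total bilirubin above 1.5 × ULN "unless the patient has known Gilbert disease". No other numerical bilirubin limit then applies. What remains is a general exclusion for a clinically significant laboratory abnormality that, in the investigator's judgment, "precludes the patient's safe participation in and completion of the study".

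Protocol 4.5.5 includes total and direct bilirubin in both the screening and the on-study chemistry panels. SAP Appendix 1 declares no departure from the analyses planned in the protocol.

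**The concern.** Two separate features of Table 8 affect what it counts.

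First, Row 3 is wider than the protocol's laboratory criterion, and the SAP does not say so. A patient with Gilbert disease may enter with bilirubin already above 2 × ULN. For that patient Row 3 can reduce to a transaminase rise alone, while a low direct fraction would keep the patient outside the protocol's criterion.

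Second, a flag defined only as a multiple of baseline stands for very different absolute levels when entry values may run up to 5 × ULN. It can count a normal value in a table of abnormal results, and it can pass over a large absolute rise in a patient who entered with raised enzymes.

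The protocol makes potential drug-induced liver injury an adverse event of special interest (AESI, Section 5.2.3). Under Protocol 6.1, Cohorts A–D have about 30 active patients each, so one patient counted or not counted moves a cohort's proportion by 1/30 = 3.3 percentage points. In Cohort E, with 112 per arm, the step is 1/112 = 0.9 points.

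**Working it through.** The plan states no figure on this point, so there is nothing to reproduce. The check applies the Table 8 rules over the range of baselines that eligibility admits, with all values in multiples of ULN.

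**Inputs from the documents:** multiples of 3 and 5 and the bilirubin limit of 2 × ULN (SAP Table 8); direct fraction of at least 35% (Protocol 5.3.5.6); entry up to 5 × ULN (Protocol 4.1.2).

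**Assumed, because the documents do not give them:** low-normal baselines of 0.25 to 0.4 × ULN, and a direct fraction of 15% in the Gilbert example.

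**1. Row 3 against the protocol's laboratory bullet.** Let A be ALT or AST above 3 × baseline, B total bilirubin above 2 × ULN, and D a direct fraction of at least 35%. Row 3 is A and B. The protocol's bullet is A and B and D. Every patient who meets the bullet therefore meets Row 3, so the difference can only add patients.

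Example: baseline ALT 0.3, on-study ALT 0.95, total bilirubin 2.5, direct fraction 15%.
- A: 0.95 / 0.3 = 3.17, above 3, met.
- B: 2.5 is above 2, met.
- D: 15% is below 35%, not met.
- Row 3 counts this patient; the protocol's laboratory bullet does not.

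**2. Absolute level at which the baseline-scaled rows fire.** The threshold is multiple × baseline.

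| Baseline (× ULN) | Row 1 fires above | Row 2 fires above |
|---|---|---|
| 0.25 (assumed) | 0.75 | 1.25 |
| 0.3 (assumed) | 0.9 | 1.5 |
| 0.4 (assumed) | 1.2 | 2.0 |
| 1 | 3 | 5 |
| 4 | 12 | 20 |
| 5 | 15 | 25 |

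Row 1 can fire on a value within normal when 3 × baseline < 1, that is, when baseline is below one third of ULN. The spread of Row 1 thresholds is 15 / 0.9 = 16.7-fold from a baseline of 0.3, or 15 / 0.75 = 20-fold from 0.25. That ratio depends on the assumed low end.

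**3. A large rise from a high baseline.** Baseline 4, on-study 11, bilirubin above 2 × ULN: 11 / 4 = 2.75, below 3. Rows 1, 2 and 3 are all unmet. Both protocol bullets also need more than 3 × baseline, so neither is met. Adding the direct-bilirubin condition would not change this, because the miss comes from the baseline scaling.

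The 5 × ULN limit applies at screening, while baseline is the last pre-treatment value. A baseline above 5 × ULN is therefore possible, and the Row 1 threshold would then exceed 15 × ULN.

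**The case against.** The strongest reply has four parts.

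- **The scaling is the protocol's own.** Protocol 5.3.5.6 sets the transaminase part against baseline in its lead sentence and in both bullets. This stands. A reader might infer that the SAP replaced a protocol rule with a looser one, but the documents do not support that. Only the direct-bilirubin condition differs between them, and bilirubin is scaled to ULN in both.
- **A broader laboratory screen is defensible.** Row 3 matches the thresholds in the protocol's lead sentence, is not labelled Hy's Law, and sits beside an AESI display that takes its definition from the protocol. This stands as a possible design, but the SAP does not state it. A reader might infer that Hy's Law cases are lost through the omission. The set argument shows that no case meeting the laboratory bullet is lost.
- **Table 8 is headed as treatment-emergent**, so bilirubin already raised at baseline might not count. This is arguable, because the SAP defines the term for adverse events but not for laboratory values. It makes the Gilbert example possible rather than certain.
- **Other displays exist.** SAP 5.4.2.2 also plans AESI by treatment group, observed and change-from-baseline summaries, shift tables for selected tests, and counts of abnormal results for each parameter at each timepoint. Protocol 5.3.5.4 requires an adverse event report for a laboratory value the investigator judges clinically significant. A reader might infer that the safety analysis as a whole would miss a rise from 4 to 11 × ULN. It would not, since the value enters the observed-value summaries and the per-parameter counts. But those displays treat one test at a time. The AESI display relies on reported events, and the definition it refers to uses the same baseline scaling. Table 8 remains the only prespecified laboratory display that takes ALT or AST jointly with bilirubin.

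**Conclusion.** The point holds as a minor one, in two parts of different standing.

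The missing direct-bilirubin condition is an unexplained discrepancy between protocol and SAP. Its effect is in one direction: Row 3 may count patients whom the protocol's laboratory criterion would not.

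The scaling to baseline alone is a limitation inherited from the protocol. The three-fold row fires above 15 × ULN for a baseline of 5 × ULN and can fire within normal for any baseline below one third of ULN. A 4-to-11 × ULN rise with bilirubin above 2 × ULN meets no row.

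The low-normal baselines and the 15% direct fraction are assumptions. The documents give neither the distribution of baseline ALT and AST nor the frequency of Gilbert disease. The number of patients affected therefore cannot be computed and could be zero. Eligibility is also not without any bilirubin safeguard in Gilbert disease: the numerical limit is waived, but investigator judgment remains.

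**What to change.** In SAP Table 8:

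1. Reconcile Row 3 with Protocol 5.3.5.6 by adding the direct-bilirubin condition, or show the row with and without it and say that the wider version is a deliberate screen.
2. Add companion rows with the same multiples scaled to ULN beside the existing rows: ALT or AST above 3 × ULN, above 5 × ULN, and above 3 × ULN with bilirubin above 2 × ULN. These are for display only. The 4-to-11 × ULN patient with bilirubin above 2 × ULN would meet all three. A patient who enters above 3 × ULN and does not change would also meet the first, so these rows should supplement the baseline-scaled rows and not replace them.

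The AESI reporting rule stays as it is; this point proposes no clinical threshold. Splitting every row by baseline enzyme status, or listing Gilbert patients separately, is not needed and would give sparse cells in arms of about 30.

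The cost is SAP wording and a few more table rows to program and read. No new data are needed.
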